6.3 Efficacy Analyses

The primary efficacy analyses will be based on the efficacy evaluable population. For each tumor indication, subjects administered the same study treatment may be combined for analysis purposes, regardless of study phase. All data from scheduled or unscheduled tumor assessments will be included in the efficacy analyses except for tumor assessments after the initiation of new anti-cancer therapy for the ORR and DoR endpoints as described in Section 4.

Sensitivity efficacy analysis may be performed based on the ITT Population if it is sufficiently different from the efficacy evaluable population and the additional analysis may be informative. Subjects with no measurable baseline disease or no evaluable post-baseline disease assessments (i.e., NE) will be considered non-responders and included in the denominator in the calculation of the ORR for the ITT population.

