9.2.5. Efficacy analysis

The primary analysis for efficacy will be based on the cohort-specific efficacy evaluable analysis set. Sensitivity analysis may include pooling additional subjects treated in Phase 1 at the same dose level in the same tumor type.

For objective response rate (ORR), the Clopper-Pearson 80% and 95% confidence intervals (CIs) will be provided. Confidence intervals adjusting for the 2-stage nature of the design may also be provided.

Duration of response (DoR) will be calculated among responders (CR and PR). The Kaplan-Meier method will be used to estimate median DoR and the confidence intervals. Subjects who continue to respond at the time of the analysis will be censored at the last assessment of response.

Progression-free survival (PFS) is measured from the date of first study treatment dose until the first date when progressive disease (PD) is objectively documented or death from any cause. Subjects without PD or death will be censored at the last available tumor assessment. PFS will be summarized using the Kaplan-Meier method.

Overall survival (OS) is measured from the date of first study treatment dose until death. Subjects who are alive will be censored at the last known alive date. OS will be summarized using the Kaplan-Meier method.

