6.1 General Statistical Considerations

In general, all analyses will be summarized by dose level and study treatment (e.g. monotherapy, combination with cemiplimab). Safety analysis will be based on the safety analysis population. The primary efficacy analysis will be based on the efficacy evaluable population by study treatment and/or tumor indication.

For each tumor indication, subjects administered the same study treatment may be combined for analysis purposes, regardless of study phase. Statistical inference, when performed, will be assessed at the 2-sided nominal 5% significance level without multiplicity adjustment. Point estimates will be accompanied by 95% confidence intervals (CIs). For the ORR endpoint assessed per the Simon's 2-stage design, the 2-sided 80% CI may be used.

For continuous variables, the number of observations (n), mean, standard deviation, median, minimum, and maximum will be provided as summary statistics. The mean and median will be reported to one additional decimal place compared to the original data. The standard deviation will be reported to two additional decimal places compared to the original data and the minimum and maximum will be reported to the same number of decimal places as the original data.

For categorical variables, the frequency and percentage in each category will be displayed. Percentages (e.g., for AEs and concomitant medications) will be calculated out of the population total for each cohort. Footnotes will clarify the denominator used in each output if other than the analysis set stated in the title. Percentages will be reported to one decimal place throughout unless the percentage is 100 (in which case no decimal places will be presented) or if the frequency count is zero (in which case no percentage will be presented).

For time to event data, unless otherwise noted, the median value, 25th percentile and 75th percentile will be calculated using the Kaplan-Meier method. The Brookmeyer and Crowley method will be used to calculate the CI of the median value (Brookmeyer and Crowley 1982). Also, the Greenwood formula will be used to calculate the CI of the rate of interest pertaining to the time to event data, at a given time point estimated using the Kaplan-Meier method (Kalbfleisch and Prentice 2002). The time to event analysis will be calculated only if an adequate number of responses are observed to warrant.

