6.3.1 Primary Efficacy Analyses

Objective Response Rate (ORR)

Point estimate of the ORR will be provided for each study treatment and/or tumor indication with the 2-sided 80% and 95% exact Clopper-Pearson CIs (Clopper and Pearson 1934) and if an adequate number of responses are observed to warrant. Confidence intervals adjusting for the 2-stage nature of the design may also be provided.

The best overall response (confirmed CR, confirmed PR, SD, PD, NE) will also be tabulated to show the number and percentage of subjects in each response category.

ORR between the monotherapy and combination therapy cohorts of the same tumor type may be compared as an exploratory analysis. The difference and its 95% CI will be provided using the continuity corrected Wilson score method (Newcombe 1998). This analysis will be calculated only if an adequate number of responses are observed to warrant.

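### The SAP lets Phase 1 subjects into the primary efficacy results without the protocol's sensitivity label or same-dose condition, and declares no change

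*SAP*

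**What the plan says.** **Protocol.** Section 9.2.5 states: "The primary analysis for efficacy will be based on the cohort-specific efficacy evaluable analysis set". Section 9.1 defines that set for each Phase 2 cohort on its own, and section 4.1.1 requires the disease cohorts to be analyzed separately. Phase 1 subjects come in only through this sentence of 9.2.5: "Sensitivity analysis may include pooling additional subjects treated in Phase 1 at the same dose level in the same tumor type".

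**SAP.** Section 6.1 states: "The primary efficacy analysis will be based on the efficacy evaluable population by study treatment and/or tumor indication". The next paragraph opens with the pooling sentence, which section 6.3 repeats straight after naming the primary efficacy population: "For each tumor indication, subjects administered the same study treatment may be combined for analysis purposes, regardless of study phase". Section 6.3.1 continues on the same footing: "Point estimate of the ORR will be provided for each study treatment and/or tumor indication". Section 3 defines study treatment as E-602 alone or E-602 with cemiplimab, so dose is not part of the term. Section 3.3 has no phase or cohort restriction. The sensitivity analysis that 6.3 names is a different one: "Sensitivity efficacy analysis may be performed based on the ITT Population if it is sufficiently different from the efficacy evaluable population".

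SAP 1 undertakes to document major modifications of the protocol's analyses. SAP 8 says there are none.

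**The concern.** The protocol sets three limits: the primary analysis belongs to the Phase 2 cohort, Phase 1 pooling is a sensitivity analysis, and pooling needs both the same dose and the same tumor type. The SAP keeps only the tumor type. Its requirement of the same study treatment separates monotherapy from combination but not one dose from another, and planned Phase 1 monotherapy runs from 1 to 30 mg/kg.

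The trial is open-label and SAP 4 uses investigator-assessed response. If the SAP does not fix the subjects behind the reported ORR, DoR, PFS and OS, the choice can be made after responses are known. A reader also cannot tell whether the SAP meant to change the protocol or is loosely worded, because SAP 8 declares nothing.

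There is a further consequence for ORR. SAP 6.1 links an interval to the design: "For the ORR endpoint assessed per the Simon's 2-stage design, the 2-sided 80% CI may be used". That interval agrees with the cohort's pass/fail result only when it is computed on the cohort's own subjects.

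**Working it through.** **1. The stated design reproduces.** Inputs from Protocol 9.4 and SAP 2.3: 16 subjects in Stage 1, continue if at least 2 respond, 31 in total, promising if at least 6 respond, null 10%, alternative 25%, type I error 0.1, power 80%.

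P(promising | p) = Σ over x₁ ≥ 2 of Bin(x₁; 16, p) × P(Bin(15, p) ≥ 6 − x₁)

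This gives 0.0788 at p = 0.10 and 0.805 at p = 0.25, as claimed. The result is for one cohort of 31 with no Phase 1 subjects.

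**2. The 80% interval matches the final rule on 31 subjects.** The Clopper-Pearson 80% lower bound for x of n is the 0.10 quantile of Beta(x, n − x + 1). The upper bound is the 0.90 quantile of Beta(x + 1, n − x). For n = 31, 5 responders give 8.1% and 6 give 10.5%. The bound rises with x, so it exceeds 10% exactly when x ≥ 6.

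**3. What adding Phase 1 subjects does.**

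| Cohort | Added | Pooled | ORR | 80% CI | Lower bound > 10%? |
|---|---|---|---|---|---|
| 6/31 | none | 6/31 | 19.4% | 10.5–31.5% | yes |
| 6/31 | 0 of 1 | 6/32 | 18.8% | 10.2–30.6% | yes |
| 6/31 | 0 of 2 | 6/33 | 18.2% | 9.8–29.7% | no |
| 7/31 | 0 of 10 | 7/41 | 17.1% | 9.8–27.0% | no |
| 5/31 | none | 5/31 | 16.1% | 8.1–27.9% | no |
| 5/31 | 2 of 6 | 7/37 | 18.9% | 10.8–29.8% | yes |

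So a cohort that passes can be shown with an interval that includes the null, and a cohort that fails can be shown with one that excludes it.

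**4. How often.** Let X₁ ~ Bin(16, p), continue if X₁ ≥ 2, and X₂ ~ Bin(15, p). The cohort passes if X₁ + X₂ ≥ 6. Add R ~ Bin(k, p) responders from k Phase 1 subjects. Disagreement means that the pass result differs from whether the 80% lower bound of (X₁ + X₂ + R)/(31 + k) exceeds 10%. Exact enumeration, conditional on reaching Stage 2:

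| True ORR | k = 0 | k = 3 | k = 6 | k = 9 |
|---|---|---|---|---|
| 10% | 0 | 7.9% | 8.0% | 9.9% |
| 15% | 0 | 12.9% | 13.1% | 16.6% |
| 20% | 0 | 11.6% | 11.8% | 14.9% |
| 25% | 0 | 7.1% | 7.1% | 8.8% |

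Both directions occur. At 15% with k = 6, the unconditional chance of a pass with a bound at or below 10% is 5.05%, and of a fail with a bound above 10% it is 4.33%. Their sum is 9.38%. Divided by the 71.6% chance of reaching Stage 2, this returns the 13.1% in the table.

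The documents give no count of same-tumor Phase 1 subjects, so k = 3, 6 and 9 are assumptions. The calculation also assumes the same true ORR in both phases and all 31 cohort subjects evaluable.

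**The case against.** The strongest reply is that the SAP wording is permissive. It says subjects may be combined, not that the primary analysis will be pooled. SAP 6.1 also opens with a default that would keep doses apart: "In general, all analyses will be summarized by dose level and study treatment". Since SAP 8 declares no changes, one can hold that Protocol 9.2.5 still governs. This stands to the extent that pooling, and mixing of doses, is possible rather than certain. It does not remove the conflict. The default is qualified by its own opening words and is a rule for display, not a condition on pooling. It also names dose level and study treatment as two separate things, so the same study treatment does not imply the same dose. SAP 1 says the SAP may modify the protocol's analyses, so a reader cannot assume that the protocol overrides it.

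On size, no passage makes the 80% lower bound a decision criterion, and both documents allow intervals adjusted for the two stages. That is correct: the comparison shows how a reported interval can contradict the cohort result, not an error in the decision rule. The percentages are conditional on Stage 2. Unconditionally they are 3.9–4.8% at a true ORR of 10%, 9.3–11.9% at 15%, 10.0–12.8% at 20% and 6.6–8.3% at 25%. Because equal response rates were assumed, they also do not measure the effect of mixing doses, which remains unquantified.

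Two points are not in dispute. The response-count decisions belong to the Phase 2 cohort (SAP 2.3 and 7.2), so no inflation of their type I error is claimed. And SAP 3.3 has to remain broad enough for the Phase 1 secondary efficacy endpoints.

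**Conclusion.** The concern holds, and the SAP should be changed. Its pooling rule contradicts the protocol that it says it does not change, on the question of which subjects form the primary efficacy results. That finding rests on the text and needs no calculation.

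The numerical effect is confined to borderline counts, and its direction cannot be known in advance. Under the assumptions stated above, a pooled 80% interval would disagree with the cohort's final result in about 7% to 17% of cohorts that complete Stage 2, against none without pooling. The go/no-go decision is not affected. What is exposed is the reported estimate and its interval.

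**What to change.** In SAP 6.1, 6.3 and 6.3.1, state that the Phase 2 primary efficacy analyses use the efficacy evaluable subjects of each Phase 2 cohort alone, with cohorts 201–203 and 211–213 kept separate. Make clear that the statement in 6.3 also covers DoR, PFS and OS in 6.3.2: SAP 2.2 lists these as Phase 2 primary endpoints, whereas 4.2 and 6.3.2 class them as secondary. Label the combination of Phase 1 and Phase 2 subjects as a sensitivity analysis limited to the same E-602 dose level, regimen and tumor type. Leave SAP 3.3 broad enough for the Phase 1 endpoints. If wider pooling is intended, declare and justify it in SAP 8.

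The cost is SAP wording and some precision in the primary interval. At an ORR of about 19%, the 80% interval is 31.5 − 10.5 = 21.0 percentage points wide on 31 subjects (6/31), against 18.9 points on 37 (7/37, 10.85% to 29.76%). No data are lost, because the Phase 1 subjects remain in the sensitivity analysis.

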6.3.1 Primary Efficacy Analyses

Objective Response Rate (ORR)

Point estimate of the ORR will be provided for each study treatment and/or tumor indication with the 2-sided 80% and 95% exact Clopper-Pearson CIs (Clopper and Pearson 1934) and if an adequate number of responses are observed to warrant. Confidence intervals adjusting for the 2-stage nature of the design may also be provided.

The best overall response (confirmed CR, confirmed PR, SD, PD, NE) will also be tabulated to show the number and percentage of subjects in each response category.

ORR between the monotherapy and combination therapy cohorts of the same tumor type may be compared as an exploratory analysis. The difference and its 95% CI will be provided using the continuity corrected Wilson score method (Newcombe 1998). This analysis will be calculated only if an adequate number of responses are observed to warrant.

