2.3 Sample Size Determination

Dose escalation for all cohorts will utilize a modified 3 + 3 design. Five dose escalation cohorts are planned for E-602 monotherapy for a total of up to 30 subjects. Two dose cohorts are planned for the E-602 and cemiplimab combination therapy for a total of up to 12 subjects. Any Phase 1 cohort may be backfilled up to 15 subjects in a dose cohort (dose escalation and backfill) to obtain additional safety, PK and pharmacodynamic data at a particular dose level.

For each cohort in Phase 2, Simon's minimax 2-stage design will be used. Sixteen subjects will be enrolled in the first stage. If ≥ 2 of 16 subjects respond, Stage 2 will be opened to enroll an additional 15 subjects for a total of 31 subjects in the cohort. At the end of Stage 2, if ≥ 6 of 31 subjects respond, the treatment will be considered promising for further evaluation. Within each cohort, the design has 80% power and a type I error rate of 0.1 to test the null hypothesis that the response rate is $\leq 10\%$ against the alternative hypothesis of $\geq 25\%$.

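### For the Simon two-stage cohorts, SAP 6.3.1 commits only to the raw ORR and fixed-sample Clopper-Pearson intervals: upper limits at low response counts are too low, and the two-stage-adjusted interval is optional with no method named

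*SAP*

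**What the plan says.** SAP 2.3 sets the design: "For each cohort in Phase 2, Simon's minimax 2-stage design will be used". The continuation rule is "If ≥ 2 of 16 subjects respond, Stage 2 will be opened to enroll an additional 15 subjects for a total of 31 subjects", and the final rule is "if ≥ 6 of 31 subjects respond, the treatment will be considered promising for further evaluation". The stated operating characteristics are 80% power at a 25% response rate and a type I error of 0.1 at 10%. Protocol 9.4 gives the same design.

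The firm analysis in SAP 6.3.1 is "Point estimate of the ORR will be provided for each study treatment and/or tumor indication with the 2-sided 80% and 95% exact Clopper-Pearson CIs". Protocol 9.2.5 matches it: "For objective response rate (ORR), the Clopper-Pearson 80% and 95% confidence intervals (CIs) will be provided". The SAP sentence adds that there must be enough responses to warrant the analysis. Both documents then allow the adjusted version: "Confidence intervals adjusting for the 2-stage nature of the design may also be provided". Neither names a method, says when it would be used, or says which interval takes precedence. Neither mentions an adjusted point estimate.

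**The concern.** Clopper-Pearson limits are exact for a fixed number of subjects. Here the number depends on the data: 0 or 1 response in 16 ends the cohort, and only cohorts with 2 or more go on to 31. A result of 2/31 under this design is not the same evidence as 2/31 from a fixed sample, because the outcomes that rank below it include every cohort that stopped. The fixed-sample calculation leaves out most of that lower tail, so its upper limit is too low.

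This affects the description of cohorts that pass Stage 1 and then end with few responses. ORR is the SAP's primary efficacy endpoint, up to six cohorts use the design, and the trial is open-label. If the interval is left optional, the choice can be made after the results are known.

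**Working it through.** **Inputs** (SAP 2.3 and 6.3.1): n1 = 16, continue if X1 ≥ 2, n2 = 15, total 31, success if X1 + X2 ≥ 6, null rate 10%, alternative 25%. Two-sided 80% and 95% intervals put 0.10 and 0.025 in each tail.

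**1. The plan's own figure.** The probability of success is the sum over a ≥ 2 of P(X1 = a) × P(X2 ≥ 6 − a), with X1 ~ Bin(16, p) and X2 ~ Bin(15, p). This gives 0.0788 at p = 10% and 0.8053 at p = 25%, consistent with the stated 0.1 and 80%. A search finds no qualifying design with 30 or fewer subjects. Of those with 31, the planned one has the smallest expected size under the null (23.28). The design is correct as stated.

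**2. Outcome probabilities.** For s = 0 or 1 (stopped): C(16,s) p^s (1−p)^(16−s). For s of 31: c_s p^s (1−p)^(31−s), where c_s is the sum over a ≥ 2 of C(16,a) C(15,s−a). Thus c_2 = 120, c_3 = 2,360 and c_4 = 22,820. At p = 25%: 0/16 has 0.0100, 1/16 has 0.0535, 2/31 has 0.0018, 3/31 has 0.0117 and 4/31 has 0.0377.

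**3. Bias of the raw ORR**, averaged over all outcomes. Its expected value is 0.0851 at p = 10% (−1.5 points), 0.1357 at 15% (−1.4), 0.1898 at 20% (−1.0) and 0.2439 at 25% (−0.6).

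**4. Upper limits.** At 2/31 the Clopper-Pearson 95% limit solves P(Bin(31, p) ≤ 2) = 0.025, so p = 0.2142. The two-stage limit under stage-wise ordering solves

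(1−p)^16 + 16p(1−p)^15 + 120p²(1−p)^29 = 0.025, so p = 0.3030.

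At p = 0.2142 the left-hand side is 0.021 + 0.092 + 0.005 = 0.118, well above 0.025. Ordering by the raw proportion ranks the outcomes the same way, because 1/16 = 6.25% is below 2/31 = 6.45%.

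The uniformly minimum variance unbiased estimate (UMVUE) at s of 31 is the sum over a ≥ 2 of C(15,a−1) C(15,s−a), divided by c_s. At 2/31 it is 15/120 = 12.5%; at 4/31 it is 3,605/22,820 = 15.8%.

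| Outcome | Raw | UMVUE | 80% upper, CP | 80% upper, two-stage | 95% upper, CP | 95% upper, two-stage |
|---|---|---|---|---|---|---|
| 1/16 | 6.3% | 6.3% | 22.2% | 22.2% | 30.2% | 30.2% |
| 2/31 | 6.5% | 12.5% | 16.3% | 22.5% | 21.4% | 30.3% |
| 3/31 | 9.7% | 14.0% | 20.3% | 23.6% | 25.8% | 30.8% |
| 4/31 | 12.9% | 15.8% | 24.1% | 25.7% | 29.8% | 32.3% |
| 5/31 | 16.1% | 18.0% | 27.9% | 28.6% | 33.7% | 34.8% |
| 6/31 | 19.4% | 20.4% | 31.5% | 31.8% | 37.5% | 37.9% |

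The Clopper-Pearson limits are out of order: a cohort stopped at 1/16 has a 95% upper limit of 30.2%, and one that passed Stage 1 and ended at 2/31 has 21.4%. The two-stage limits keep the order.

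**5. Where the conclusion about 25% changes.** Only at 2/31 for the 95% interval (21.4% against 30.3%) and at 4/31 for the 80% interval (24.1% against 25.7%). At 3/31 both 95% intervals include 25% and both 80% intervals exclude it.

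**6. Error rates of Clopper-Pearson under the two-stage design.**
- At true 25%, the 80% upper limit falls below 25% with probability 0.0100 + 0.0535 + 0.0018 + 0.0117 + 0.0377 = 0.1147 (nominal 0.10; two-stage 0.0770).
- At true 25%, the 95% upper limit falls below 25% at 0/16 and 2/31: 0.0100 + 0.0018 = 0.0118 (nominal 0.025; two-stage 0.0100).
- The largest upper-side miss over all p is 13.4%, just above p = 24.15% (80% interval), and 3.95%, just above p = 30.2% (95% interval).
- The lowest two-sided coverage is 80.3% and 95.0%.

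**The case against.** The strongest reply is that the plan already foresees the adjustment and promises only two-sided intervals, whose coverage never drops below nominal. That stands. What remains is a specification gap: an option with no method.

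A reader might infer that the plan will often rule out the 25% target wrongly. The figures do not support this. A wrong exclusion needs a true rate of at least 25%. At exactly 25%, the two outcomes where the conclusion changes have probability 0.18% and 3.8%. The total 95% upper-side miss there is 1.2%, below nominal. Among cohorts that passed Stage 1, the miss rates at 25% are 0.19% (95%) and 5.5% (80%), both below nominal. The 13.4% and 3.95% peaks are narrow spikes caused by discreteness.

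A reader might also infer that the go/no-go decision is affected. It is not: both documents decide on the response count, and no section uses a confidence limit to judge compatibility with 25%.

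Replacing the raw ORR by the UMVUE would go too far. At 2/31 the UMVUE equals 2/16, so the 15 Stage 2 non-responders do not lower it. It is unbiased over all outcomes, not among cohorts that continue. Among those, the raw ORR averages 13.3% at a true 10% and 25.7% at a true 25%, above the truth. This is why the adjusted results belong beside the raw ones.

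**Conclusion.** The concern holds in a limited form. The committed interval does not match the sampling design. Its upper limits are too low at small counts, by 8.9 points at 2/31 (95%) and about 1.6 points at 4/31 (80%), and they rank a cohort that passed Stage 1 below one that failed it. The raw ORR is biased slightly downward over all outcomes. From 6/31 upward the limits differ by under 0.5 points (at 6/31, 37.5% against 37.9%), and the UMVUE at 6/31 is about 1 point above the raw proportion. The design, the count rule and two-sided coverage are sound. This is a worthwhile tightening of the SAP, not a flaw that endangers the trial's conclusions.

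The figures assume exactly 16 and 31 analysed subjects and the continuation rule applied as written. That may not hold. The efficacy evaluable population requires a post-baseline assessment (SAP 3.3), Phase 2 subjects are not replaced (Protocol 7.1.2), and SAP 6.3 allows pooling across phases. The documents do not say how an adjusted interval would be computed in those cases.

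**What to change.** In SAP 6.3.1, for each Phase 2 Simon cohort, turn 'may' into 'will' for the adjusted interval and name the method:

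- Exact 80% and 95% intervals from the two-stage sampling distribution under stage-wise ordering, with any outcome that stops at Stage 1 ranked below every outcome that continues.
- The UMVUE as a bias-corrected estimate.
- Both reported alongside the raw proportion and Clopper-Pearson intervals, which stay in place.
- Computed on the Phase 2 cohort without pooled Phase 1 subjects, using the actual stage sizes if they differ from 16 and 31.

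It would help to state that the condition about having enough responses does not apply to these results, since they matter most when responses are few.

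The cost is a few sentences and a few lines of code. The protocol already permits the adjustment, and design, sample size and conduct do not change. The downside is a second, less familiar estimate that differs from x/31 when responses are few and needs a sentence of explanation in the report.
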